### **5.3. Analyses for recruitment, retention and data quality**

Monthly recruitment statistics will be generated for the study as a whole and by clinical site. Run charts will plot cumulative recruitment and anticipated recruitment rates required to fully enroll the clinical trial according to the study timeline. Tabular data will be provided for the number of screen failures and the number of participants withdrawing from the study before week six and without reaching a study endpoint (i.e. lost to follow-up).

Tabular in distribution data will be generated to monitor data completeness and quality. Tables will describe the number of participants for whom eCRF data are incomplete, overall and stratified by study site. Baseline characteristics data and components of the sCDAI will be generated to identify outliers that may represent data entry errors. These data points will be confirmed or corrected by queries to the clinical site coordinators. Variables for which distributions will be generated will include: age, height, weight, body mass index, duration of Crohn's disease, and time since onset of the most recent flare of Crohn's disease. Additional data will be evaluated for illogical values or protocol violations including: baseline sCDAI score, current dose of prednisone, serum albumin, and body mass index.

### **5.4. Analysis of Baseline Data**

The initial analyses will utilize descriptive statistics to define the characteristics of the study cohort. Continuous variables will be described as medians and interquartile ranges. Categorical variables will be defined as proportions. Formal statistical comparisons of these descriptive variables will be performed comparing the two arms of the study using the Wilcoxon rank sum test for continuous variables and the chi squared or Fisher's exact test for categorical variables. Because any unbalance in the two groups is by definition a chance occurrence, these analyses will be used to highlight areas of substantial unbalance between the study arms.

### **5.5. Efficacy Analysis**

Analysis of the primary outcome: The primary outcomes will be measured at 6 weeks after the start of the study diets. The primary analyses for the RCT will use 2-sided tests of statistical significance and will be performed using the intention-to-treat principle. Thus, patients will be classified according to the study arm that they were assigned, regardless of the amount of food from the assigned diet consumed.

#### **5.5.1. Outcome definitions**

Clinical remission will be defined use the sCDAI which provides a composite measure of relevant patient reported outcomes (PROs). Symptomatic remission will be defined as a sCDAI <150^4 in the absence of the need for increasing corticosteroid dose or initiation of new therapies for CD during the study period. Participants who withdraw from the study prior to week 6 will be categorized as failing to achieve symptomatic remission and other related outcomes.

##### **5.5.1.1. sCDAI**

The sCDAI was derived from the Crohn's Disease Activity Index, the standard disease activity index for CD clinical trials in adults for the last several decades. The original index includes the number of liquid stools per day, abdominal pain, general wellbeing, extraintestinal complications of CD, use of Lomotil or opiates for diarrhea, anemia, weight loss, and the presence of an abdominal mass on physical exam. The CDAI has increasingly fallen out of favor as it combines PROs with physical exam, medication use, and laboratory data. As such, investigators validated the sCDAI which patients can complete using a simple web-based survey tool without an office visit or blood draw. The sCDAI uses the same scale as the full CDAI, such that scores <150 define remission, 150-219 mild activity, 220-450 moderate activity, >450 severe activity. The correlation between the full CDAI and sCDAI for baseline scores and score change was 0.90 and 0.96, respectively. Our research team has subsequently demonstrated that the sCDAI can be accurately measured with less than 7 days of data, thereby reducing participant burden and allowing for use of data with missing values for selected days.

Computation is straightforward:

$$sCDAI = 44 + \left( 2 * \sum_{n=1}^7 L \right) + \left( 5 * \sum_{n=1}^7 A \right) + \left( 7 * \sum_{n=1}^7 W \right)$$

where  $L$  is the number of liquid stools,  $A$  is the rating of abdominal pain (0-3, none to severe),  $W$  is the rating of general wellbeing (0-4, generally well to terrible), and  $n$  is the day of follow-up.

Similarly, when computing the sCDAI scores for fewer than 7 days, the individual component scores from the available days can be weighted to take on the value as if there were 7 days of data and the available data are considered to be reflective of the missing data. The computation is to multiply the sum of the individual components by 7 and divided by the number of total days of data used ( $d$ ) to adjust for the missing days:

$$sCDAI = 44 + \frac{7}{d} * \left( \left( 2 * \sum_{n=1}^d L \right) + \left( 5 * \sum_{n=1}^d A \right) + \left( 7 * \sum_{n=1}^d W \right) \right)$$

### 5.5.1.2. Secondary Endpoints

#### 5.5.1.3. Reduction in fecal calprotectin

We will compare the proportion of patients who achieve reduction in FCP to less than 250mcg/g and by greater than 50% from baseline. Fecal concentration of calprotectin, a calcium binding protein found in neutrophilic granulocytes, will be measured by LabCorp Diagnostics. FCP concentration is correlated with endoscopic findings of mucosal inflammation and decreases following initiation of medications in active CD. There is no single standard to define mucosal healing with FCP; a recent meta-analysis identified 250 µg/g as the optimal cut point for endoscopically defined inflammation among patient with IBD. **Participants with a baseline FCP less than 250mcg/g will be excluded from this analysis.**

##### 5.5.1.3.1. Reduction in systemic inflammation

Reduction in systemic inflammation based on measurement of hsCRP will be defined as having a final hsCRP <5mg/L and >50% reduction from the baseline hsCRP concentration.

##### 5.5.1.3.2. Crohn's Disease Activity Index (CDAI)

As a secondary clinical outcome, we will measure the CDAI at baseline, 6 weeks and 12 weeks. Computation of the CDAI is the sum of the following components over the course of 7 days and multiplied by the weighting factor:

Variable	Weighting factor
Number of liquid or soft stools each day for seven days	x 2
Abdominal pain (graded from 0-3 on severity) each day for seven days	x 5
General well being, subjectively assessed from 0 (well) to 4 (terrible) each day for seven days	x 7
Presence of complications*	x 20
Taking Lomotil or opiates for diarrhea	x 30
Presence of an abdominal mass (0 as none, 2 as questionable, 5 as definite)	x 10
Hematocrit below normal of 0.47 in men and 0.42 in women	x 6
Percentage deviation from standard weight^	x 1

\*One point each is added for each set of complications:

- the presence of joint pains ([arthralgia](#)) or frank [arthritis](#)
- inflammation of the [iris](#) or [uveitis](#)
- presence of [erythema nodosum](#), [pyoderma gangrenosum](#), or [aphthous ulcers](#)
- [anal fissures](#), [fistulae](#) or [abscesses](#)
- other [fistulae](#)
- [fever](#) during the previous week.

^ Standard weight is derived from the patients sex and height

CDAI remission will be defined as a CDAI<150 in the absence of the need for increasing corticosteroid dose or initiation of new therapies for CD during the study period

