### **2.2 Primary Objectives**

1. To compare the effectiveness of the Specific Carbohydrate Diet and a Mediterranean style diet to induce symptomatic and clinical remission in patients with Crohn's disease.
  - Hypothesis 1. Patients following the SCD will be more likely to experience resolution of CD symptoms than patients following a MSD.
- 2.

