## **4 Study Population and Duration of Participation**

### **4.1 Inclusion Criteria**

1. Age ≥18
2. Documented diagnosis of Crohn's disease
3. sCDAI score >175
4. Documentation of receipt of a baseline stool sample by the data coordinating center and hsCRP.

5. Access to a computer with internet and the ability to complete daily online surveys
6. Capable of providing consent to participate
7. Able to receive weekly food shipments delivered every Friday for 6 weeks

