### 2. Overview

This is a randomized, multicenter, comparative effectiveness trial of the specific carbohydrate diet (SCD) and a Mediterranean style diet (MSD) to induce remission in patients with Crohn's disease. The study is funded by PCORI, will be conducted in up to 50 centers throughout the United States over a period of three years.

The primary and secondary objectives of this clinical trial are the following:

*Primary:*

1. To compare the effectiveness of the specific carbohydrate diet and a Mediterranean style diet to induce symptomatic and clinical remission in patients with Crohn's disease.
- 2.
3. *Secondary:*
  1. To compare the effectiveness of the specific carbohydrate diet and a Mediterranean style diet to reduce mucosal inflammation in patients with active Crohn's disease. Mucosal inflammation will be assessed by measuring the concentration of calprotectin in the feces (FCP).
  2. To compare the effectiveness of the Specific Carbohydrate Diet and a Mediterranean style diet to reduce systemic inflammation in patients with active Crohn's disease. Systemic inflammation will be assessed by measuring the concentration of C reactive protein (CRP).
  3. To compare the effectiveness of the specific carbohydrate diet and a Mediterranean style diet to improve the following symptoms in patients with Crohn's disease: a) fatigue, b) pain, c) joint symptoms.
  4. To determine the proportion of patients who continue the study diets when prepared food is no longer provided without cost and the reasons for discontinuation of the diets.

The clinical trial will enroll 194 participants who will be randomly assigned in a 1 to 1 ratio to the two study diets. The main inclusion criteria are Crohn's disease with mild to moderately active symptoms as measured by the short CDAI (sCDAI) score greater than 175 and less than 400, and at least 18 years of age. The main exclusion criteria are the following:

- Pregnancy
- Hospitalized pts. or surgery planned within 6 wks
- Ostomy or known symptomatic intestinal stricture
- Start of thiopurines, natalizumab, vedolizumab or methotrexate (w/in 12 wks) or anti-TNF (w/in 8 wks)
- Start or change corticosteroids within 1 week of screening or dose >20mg prednisone or equivalent
- Use of antibiotics w/in 2 weeks of screening
- Start or change of dose of 5-ASA type medication w/in 2 weeks of screening
- Baseline stool frequency >4 bowel movements/day when well
- BMI<16 or ≥40

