#### **5.5.1.3.3. PRO2 and PRO3**

The same data elements included in the sCDAI have been combined into two item (stool frequency and abdominal pain) and three item patient reported outcome measures using the original weights derived from the full CDAI. PRO2 includes only stool frequency and abdominal pain while PRO3 includes stool frequency, abdominal pain and general well-being. These outcome measures are calculated as the sum of the mean of the daily value for each domain.

PRO2 = mean daily soft or loose stool frequency + mean abdominal pain score

PRO3 = mean daily soft or loose stool frequency + mean abdominal pain score + mean general wellbeing score

In one validation study of the PRO2 and PRO3, optimum cut-points for CDAI remission were mean daily stool frequency  $\leq$ 1.5, abdominal pain  $\leq$ 1, and general well-being score of  $\leq$ 1 (areas under the ROC curve 0.79, 0.91 and 0.89, respectively). PRO2 and PRO3 values corresponding to CDAI scores of 150, 220, and 450 points were 8, 14, and 34 and 13, 22, and 53 respectively, and the corresponding values for CDAI changes of 50, 70, and 100 points, were 2, 5, and 8 and 5, 9, and 14, respectively. We will examine the individual components of these PROs to determine the proportion of each group that met the optimum cutpoint for remission that met the PRO2 definition of remission. Finally, we will determine the proportion of each group with a reduction in the PRO2 and PRO3 that corresponds to 100 point reduction in the CDAI.

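### Participants can enter already meeting the CDAI or PRO2 remission criterion, and the plan counts that unchanged state at week 6 as a remission

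*Combined protocol and SAP*

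**What the plan says.** **Entry.** Protocol 4.1 requires "sCDAI score >175", and 4.2 excludes scores above 400. Section 2 of the SAP (Appendix G) restates the range as "short CDAI (sCDAI) score greater than 175 and less than 400, and at least 18 years of age". No entry criterion refers to CDAI or PRO2.

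**CDAI.** SAP 5.5.1.3.2 states "we will measure the CDAI at baseline, 6 weeks and 12 weeks", so the baseline value will be available. The score is built as follows: "Computation of the CDAI is the sum of the following components over the course of 7 days and multiplied by the weighting factor". The outcome is "CDAI remission will be defined as a CDAI<150 in the absence of the need for increasing corticosteroid dose" or for starting a new Crohn's therapy. Protocol 3.4.2.1 and 8.2 define it the same way. None of these places asks that CDAI was 150 or more at baseline, or that it fell by any amount.

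**PRO2.** SAP 5.5.1.3.3 gives cut-points of 1.5 for mean daily stools and 1 for pain and for wellbeing, and a PRO2 value of 8 as the counterpart of CDAI 150. It plans to "determine the proportion of each group that met the optimum cutpoint for remission that met the PRO2 definition of remission". Again there is no baseline condition.

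**Analysis.** Protocol 8.4.2 and SAP 5.5.2 apply the primary-outcome methods to CDAI and PRO2 remission. Protocol 8.5 includes everyone randomised. By contrast, SAP 5.5.1.3 leaves participants with baseline FCP below 250 out of the FCP responder analysis.

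**Objective.** Protocol 2.2 compares the ability of the diets to "induce symptomatic and clinical remission in patients with Crohn's disease".

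**The concern.** The trial asks about induction. An induction outcome should count people who moved into remission, so a participant must be outside that state at the start. For the primary outcome the entry rule secures this. For CDAI and PRO2 remission it may not, because eligibility is judged on one index and success on another.

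If some participants start below the CDAI or PRO2 cut, those who do not change are scored as remissions in whichever arm they are in. Both reported rates then overstate what the diets induced, and the contrast between diets is likely to shrink, because these participants carry little information about induction.

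**Working it through.** **1. The plan's own power figure.** SAP 5.2 states 80% power with 97 per arm for 40% versus 60%, chi-square test, type 1 error 5%; SAP 5.5 makes the tests two-sided. The uncorrected chi-square calculation gives 80.03%, so the figure is reproduced and is used as the reference below.

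**2. CDAI at the entry boundary.** Let D be the weighted diary sum over seven days: 2 × stools + 5 × pain + 7 × wellbeing.
- SAP 5.5.1.1: sCDAI = 44 + D.
- SAP 5.5.1.3.2: CDAI = D + X, where X totals the other items (20 per complication, 30 for antidiarrhoeals, 10 × mass score, 6 per point of hematocrit deficit, 1 × weight deviation).
- On the same diary days, CDAI = sCDAI − 44 + X.

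CDAI is below 150 when sCDAI < 194 − X. Entry needs sCDAI > 175, so the overlap exists when X < 19. In whole numbers:

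| X | eligible sCDAI with CDAI < 150 |
|---|---|
| 0 | 176–193 (CDAI 132–149) |
| 6 | 176–187 |
| 12 | 176–181 |
| 20 or 30 | none |

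Example: one liquid stool, pain 1 and wellbeing 2 every day give D = 7 × (2 + 5 + 14) = 147. Then sCDAI = 191, which is eligible, and CDAI = 147 with X = 0, which is already remission.

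**3. PRO2 and the component cut-points.** With the CDAI weights, PRO2 = 2L + 5A on daily means (L stools, A pain, W wellbeing). At PRO2 = 8, sCDAI = 44 + 7 × (8 + 7W) = 100 + 49W. This exceeds 175 once W > 75/49 = 1.53 and reaches 296 at W = 4. The participant in step 2 has PRO2 = 7. Stools 1.5 and pain 1 meet both component cut-points; with wellbeing 2, sCDAI = 44 + 7 × (3 + 5 + 14) = 198. The stool cut-point alone can be met at sCDAI = 44 + 7 × (3 + 15 + 28) = 366.

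The SAP says the original CDAI weights are used but writes PRO2 as an unweighted sum, and this matters. Take constant-day diary patterns with L 0–15, A 0–3 and W 0–4. Of the 224 that are eligible, 18 meet PRO2 ≤ 8 with weights and 111 without. These are counts of patterns, not of patients.

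**4. Outcomes not affected.** The primary outcome needs sCDAI < 150 from an entry above 175. For weighted PRO3, sCDAI > 175 means 2L + 5A + 7W > 131/7 = 18.7, above the cut of 13. The PRO2/PRO3 reduction equivalent to 100 CDAI points requires change.

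**5. Illustration of size.** The documents give no share f already in remission at baseline. Assume 40% versus 60% among the rest, and that 80% of those already in remission are so at week 6 in both arms. Each arm's rate is (1 − f) × p + f × 0.80, and the difference is 20 × (1 − f) points.

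| f (assumed) | rates, all randomised | difference | power | power if restricted (20 points, about n per arm) |
|---|---|---|---|---|
| 5% | 42% vs 61% | 19 | 76% | 78% (92) |
| 10% | 44% vs 62% | 18 | 71% | 76% (87) |

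Replacing 80% by 60% or 100% leaves these power figures within half a point.

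**The case against.** The case against rests on reach and size, and much of it stands.

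- Only secondary outcomes are involved, and protocol section 2 calls the secondary aims exploratory. The plan claims no power for CDAI or PRO2 remission; the 80% in SAP 5.2 refers to symptomatic remission and FCP.
- The CDAI window is narrow. One complication, including simple joint pain, or antidiarrhoeal use closes it, as does a hematocrit four points below the reference value (6 × 4 = 24).
- A reader might infer that these participants are automatic successes. They are not: they fail if they worsen past the cut, need more steroid or a new therapy, or withdraw. If the diets differ in how well they prevent worsening, the dilution is smaller than in the table.
- A reader might infer that the clinical remission named in the primary objective does not measure induction. The documents use that label for both indices: protocol 3.4.2.1 ties it to CDAI, but SAP 5.5.1 and 5.5.1.4 tie it to sCDAI, where the entry rule does secure induction.
- The plan already has change-based measures, namely the 100-point-equivalent reduction and the paired tests in SAP 5.5.2. The paired tests are run within each arm, though, and do not name CDAI, so they do not replace a between-arm induction outcome.

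What remains is that the CDAI and PRO2 remission outcomes have no baseline condition, although the SAP applies one to FCP.

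**Conclusion.** The point holds for CDAI remission, PRO2 remission and the stool and pain cut-points. An eligible participant can already be in the state that week 6 scores as a remission, and the plan analyses that state in everyone randomised. Both arms' rates are raised to the extent that such participants stay there, and the difference is probably diluted.

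It should not be read as a threat to the primary result, or as a bias toward either diet. Randomisation makes the share similar in expectation, so type I error is not inflated.

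No prevalence can be derived from the documents. The 5–10% range is an assumption, and so is equal retention in both arms; on those terms the loss is 1–2 points of difference, and restricting the analysis recovers about 2–5 points of power. The CDAI bounds also assume that sCDAI and CDAI use the same diary days and that no item in X is negative. The SAP sets no sign or cap for weight deviation; at an assumed X of −10 the window would be 176–203.

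This is a cheap improvement to secondary outcomes, not a design flaw.

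**What to change.** 1. In SAP 5.5.1.3.3, first settle whether PRO2 is weighted, and whether a value of exactly 8 counts as remission. The baseline rule depends on both.
2. In SAP 5.5.1.3.2, analyse CDAI remission at week 6 among participants with baseline CDAI of 150 or more.
3. In SAP 5.5.1.3.3, analyse PRO2 and each component among participants not already meeting that cut-point at baseline.
4. Tabulate by arm how many were already in each state, and keep the all-randomised result alongside.
5. Leave the sCDAI primary outcome as it is.

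The restriction uses only baseline values that are already collected, so it preserves the randomised comparison and follows the SAP's own practice for FCP. The cost is SAP wording, plus smaller denominators that differ between these secondary outcomes and make them harder to set beside the primary result; the all-randomised table covers that.

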#### **5.5.1.3.3. PRO2 and PRO3**

The same data elements included in the sCDAI have been combined into two item (stool frequency and abdominal pain) and three item patient reported outcome measures using the original weights derived from the full CDAI. PRO2 includes only stool frequency and abdominal pain while PRO3 includes stool frequency, abdominal pain and general well-being. These outcome measures are calculated as the sum of the mean of the daily value for each domain.

PRO2 = mean daily soft or loose stool frequency + mean abdominal pain score

PRO3 = mean daily soft or loose stool frequency + mean abdominal pain score + mean general wellbeing score

In one validation study of the PRO2 and PRO3, optimum cut-points for CDAI remission were mean daily stool frequency  $\leq$ 1.5, abdominal pain  $\leq$ 1, and general well-being score of  $\leq$ 1 (areas under the ROC curve 0.79, 0.91 and 0.89, respectively). PRO2 and PRO3 values corresponding to CDAI scores of 150, 220, and 450 points were 8, 14, and 34 and 13, 22, and 53 respectively, and the corresponding values for CDAI changes of 50, 70, and 100 points, were 2, 5, and 8 and 5, 9, and 14, respectively. We will examine the individual components of these PROs to determine the proportion of each group that met the optimum cutpoint for remission that met the PRO2 definition of remission. Finally, we will determine the proportion of each group with a reduction in the PRO2 and PRO3 that corresponds to 100 point reduction in the CDAI.

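### The SAP says PRO2 and PRO3 carry the CDAI weights, but its printed formulas leave them out, so falls of 8 and 14 would be applied to the wrong scale

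*Combined protocol and SAP*

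**What the plan says.** Appendix G 5.5.1.3.3 describes two-item and "three item patient reported outcome measures using the original weights derived from the full CDAI". Protocol 3.4.2.2 and 8.2 also say that the CDAI weights apply, but neither prints a formula. The weights are in the CDAI table in Appendix G 5.5.1.3.2: 2 for stools, 5 for abdominal pain, 7 for general wellbeing.

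Section 5.5.1.3.3 then gives a different rule: "These outcome measures are calculated as the sum of the mean of the daily value for each domain". The PRO2 line reads "PRO2 = mean daily soft or loose stool frequency + mean abdominal pain score". The PRO3 line adds mean wellbeing, again without a weight. These are the only explicit PRO2 and PRO3 formulas in the documents.

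The same section takes reference values from a validation study. It states that "PRO2 and PRO3 values corresponding to CDAI scores of 150, 220, and 450 points were 8, 14, and 34" for PRO2, with 13, 22 and 53 for PRO3. For change, "the corresponding values for CDAI changes of 50, 70, and 100 points, were 2, 5, and 8 and 5, 9, and 14". It plans to report, per group, the proportion with a "reduction in the PRO2 and PRO3 that corresponds to 100 point reduction in the CDAI", which means falls of 8 and 14.

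**The concern.** The section gives two scoring rules that cannot both be followed, and the explicit one does not fit the thresholds attached to it. Three planned results depend on the score:

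- the proportion in each group with a fall equivalent to 100 CDAI points (protocol 3.4.2.2 and 8.2, Appendix G 5.5.1.3.3);
- the within-arm signed-rank tests of PRO2 and PRO3 against baseline (protocol 8.4.2, Appendix G 5.5.2);
- remission by PRO2 and PRO3, listed among the secondary outcomes in the same two sections, if composite thresholds of 8 and 13 are intended.

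The third is conditional. No composite remission threshold is stated, and the wording "met the optimum cutpoint for remission that met the PRO2 definition of remission" can be read as referring to the single-item cut-points, which weighting does not touch.

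**Working it through.** **Inputs.** Let L, A and W be mean daily liquid or soft stools, abdominal pain and wellbeing. Appendix G 5.5.1.1 grades pain 0–3 and wellbeing 0–4, and its equation is equivalent to sCDAI = 44 + 7(2L + 5A + 7W). Eligibility is sCDAI above 175 and below 400 (Appendix G, section 2).

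- Printed: PRO2 = L + A; PRO3 = L + A + W.
- Weighted: PRO2 = 2L + 5A; PRO3 = 2L + 5A + 7W = (sCDAI − 44)/7.

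**Which scale the quoted values are on**

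| Check | SAP value | Weighted | Printed |
|---|---|---|---|
| PRO3 fall for 100 points | 14 | 100/7 = 14.3 | no fixed conversion |
| PRO2 at single-item cut-points (1.5, 1) | 8 (at CDAI 150) | 2×1.5 + 5×1 = 8 | 2.5 |
| PRO3 at single-item cut-points (1.5, 1, 1) | 13 (at CDAI 150) | 8 + 7×1 = 15 | 3.5 |
| Stools a day needed for PRO2 = 34 with worst pain | – | (34 − 15)/2 = 9.5 | 34 − 3 = 31 |
| Stools a day needed for PRO3 = 53 with worst pain and wellbeing | – | (53 − 15 − 28)/2 = 5 | 53 − 3 − 4 = 46 |

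The weighted match is approximate. Taking sCDAI for CDAI, 150, 220 and 450 convert to weighted PRO3 of 15.1, 25.1 and 58.0 against the quoted 13, 22 and 53. Changes of 50, 70 and 100 convert to 7.1, 10 and 14.3 against 5, 9 and 14. Gaps of this kind are plausible because the full CDAI has further items. The printed scale is not close at any point that can be checked.

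**Effect on response: one participant.** From (4, 2, 2) to (1, 0.5, 0.5), sCDAI goes from 44 + 7×32 = 268 to 44 + 7×8 = 100.

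- Printed: PRO2 6 to 1.5, a fall of 4.5; PRO3 8 to 2, a fall of 6. Non-response on both.
- Weighted: PRO2 18 to 4.5, a fall of 13.5; PRO3 32 to 8, a fall of 24. Response on both.

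**Who can respond at all under the printed formulas**

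- A PRO2 fall of 8 needs L + A ≥ 8 at baseline. With A ≤ 3, that means at least 5 loose stools a day.
- A PRO3 fall of 14 needs L + A + W ≥ 14, while eligibility requires 2L + 5A + 7W < (400 − 44)/7 = 50.86. With A = 3, L + W = 11, so 37 + 5W < 50.86. Hence W < 2.77 and L > 8.23.
- At either minimum the follow-up score must be zero.

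**How demanding the rule becomes.** One printed unit costs 14 sCDAI points through stools, 35 through pain and 49 through wellbeing, so stools are the cheapest route. With no item worsening, printed falls of 8 and 14 equal at least 8×14 = 112 and 14×14 = 196 sCDAI points. Weighted falls of 8 and 14 equal at least 8×7 = 56 and 14×7 = 98. The printed rule is twice as demanding at its easiest.

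**Attainability over eligible integer profiles.** With stools capped at 10 a day (an assumption) there are 165 eligible combinations of L, A and W. A PRO2 fall of 8 is attainable in 150 weighted and 72 printed; a PRO3 fall of 14 in 165 weighted and 7 printed. Without the cap there are 262 profiles: 247 against 169, and 262 against 94. These are counts of score combinations, not of patients.

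**Direction of change.** From (5, 1, 2) to (3, 2, 2), sCDAI rises from 247 to 254. The printed scores improve by 1 (PRO2 6 to 5, PRO3 8 to 7). The weighted scores worsen by 1 (15 to 16, 29 to 30). The two versions are therefore not rescalings of each other, and a rank test is not protected.

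**Remission, only if 8 and 13 are the intended thresholds.** Before any treatment, printed PRO2 is already below 8 in 93 of the 165 capped profiles (weighted: 15). Printed PRO3 is already below 13 in 146 (weighted: 0).

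**The case against.** The strongest reply is that this is a drafting slip. The weights are stated in words in three places and tabulated in the preceding SAP section, so a programmer who follows the words gets the right scores. Appendix G 3.3 also requires the analytic plan to be agreed before the final analyses. That is fair, but the only explicit formulas say otherwise, and the choice should not be left to whoever writes the code.

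The stakes are limited. Protocol section 2 calls the secondary aims exploratory. The 100-point response is described as a proportion to be determined and is not in the list of tested outcomes. Both arms would be scored in the same way, and no bias between arms has been shown. All of this stands and limits the severity.

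The evidence on scale is partly inferential. The validation study is not available, the PRO3 conversions miss by a few points, and the exact match at 8 compares single-item cut-points with a composite value, two different derivations. What carries the conclusion is the stated weighting together with the implausible 31 and 46 stools a day.

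Finally, some gaps can be filled from elsewhere. PRO2 and PRO3 share the sCDAI's data items, whose five-to-seven-day rule is in protocol 6.2.2, and 8 and 14 are already printed as the equivalents of 100 points. Restating these is tidying, not correction of an error.

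**Conclusion.** The concern holds. Appendix G 5.5.1.3.3 contradicts itself, and its printed formulas are the wrong side of the contradiction for the thresholds it quotes. Programmed as printed, they make the response criterion at least twice as demanding in sCDAI terms when no item worsens, put a PRO3 response out of reach for any eligible participant below about 8.2 loose stools a day at baseline, and reverse the sign of some changes.

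The effect on the trial's reported proportions cannot be quantified without a baseline item distribution. The remission consequence depends on thresholds the plan does not state. The conclusion assumes that the quoted values belong to daily means weighted 2, 5 and 7. The primary sCDAI endpoint, the single-item cut-points and the sample size are unaffected. This should be fixed before programming.

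**What to change.** In Appendix G 5.5.1.3.3, replace the sentence on summing means and both formula lines with:

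- PRO2 = 2 × mean daily liquid or soft stools + 5 × mean daily abdominal pain;
- PRO3 = PRO2 + 7 × mean daily general wellbeing;
- both computed over the same days as the sCDAI.

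State the response criteria as falls of at least 8 (PRO2) and at least 14 (PRO3). State the remission rule: either the single-item cut-points alone, or composite thresholds with their values. If 13 is chosen for PRO3, note that a weighted PRO3 of 13 or less corresponds to sCDAI of 44 + 7×13 = 135 or less, which is stricter than the primary criterion of below 150. Reword the sentence that runs the single-item cut-points and PRO2 remission together.

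Add a programming check that sCDAI = 44 + 7 × PRO3 for every participant and visit, using the same days.

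The cost is one sentence and two formula lines corrected, with one or two sentences added. The daily items are already collected.
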